**EFFECTS OF A PHYSICAL EXERCISE PROGRAM ON CARDIOVASCULAR,
METABOLIC, PHYSICAL FITNESS AND QUALITY OF LIFE IN CANCER
SURVIVORS' ADULT WOMEN**

Date: December 27th, 2024

Study documents

SCIENTIFIC BACKGROUND: In Chile, in the year 2022, it was reported that the main causes of death are diseases of the circulatory system (31,606) and cancer (with 28,453 deaths) (1). Both causes of death come from diseases such as arterial hypertension, diabetes, obesity, highly linked to sedentary lifestyles (i.e., spending long hours sitting), physical inactivity (i.e., not adhering to the international recommendations of physical activity per week of 150 to 300 min of low to moderate intensity physical activity, or 75 to 150 min of vigorous physical activity per week) (2) and lifestyle (i.e., healthy eating, and inflammation processes such as cancer). Worryingly, in the Bío-Bío region alone, women's deaths from cancer reported 1,380 deaths, one of the highest in the country (3).

Exercise training (i.e., defined as a particular type of physical activity guided by a professional and regulated overtime) has demonstrated evidence of the prevention and treatment of cancer (4), as well as in diabetes and arterial hypertension (co-morbidities). This has been raised by the American College of Sports Medicine (ACSM) (4), emphasizing the evidence in favor of the practice of exercise training (i.e., particularly aerobic and strength-type exercise) from the strongest (anxiety, depression, fatigue, quality of life, lymphedema, physical function) to the least amount of evidence (cardio-vascular, pain, etc).

Despite the “solid” evidence in favor of the effects of exercise training in cancer survivors (CS) to improve variables such as anxiety, depressive symptoms, fatigue, quality of life, lymphedema, and physical function, unfortunately they are still unknown and there is minimal evidence about the effects of exercise training on cardio-vascular and metabolic variables in cancer survivors’ persons (4). The phenomenon of the exercise training in CS persons is of relevance, because as it is pointed out, cancer is the second cause of death in Chile, and in particular breast cancer is the first cause among all types of cancer, and where the exercise training has a relevant value as a treatment and post-

treatment. Thus, it is required to fill the scientific gap in terms of the need to increase the evidence of exercise training in cardio-vascular physiology, such as parameters related to blood pressure (5), and endothelial dysfunction such as carotid intima-media thickness (cIMT), dilation-mediated flow (FMD) and pulse wave velocity (PWV) (6), as well as metabolic factors related to metabolism during exercise of oxidative and glycolytic type, which determine the oxidation of fat and glucose during exercise. There is consolidated or “solid” evidence (7), about the effects of physical exercise (i.e., exercise guided by a professional and planned over time), according to the American College of Sports Medicine (ACSM) exercise recommendations guide for CS (4).

Different types of exercise training modalities have been reported in CS individuals during and following the completion of their treatment (Radiotherapy, Chemotherapy, Hormonal therapy), where the benefits of aerobic nature exercise training predominantly (i.e., exercises that promote an increase in aerobic enzymatic activity, mitochondrial biogenesis and in general oxidative metabolism [that promote the elaboration of ATP via fatty acids]) in combination with muscle strength as resistance training with the use of external overloads (i.e., controlled exercises with a certain level of muscle load based on prior assessment of maximal strength, usually measured by means of 1-repetition maximal test on different muscle groups), which are exercises that promote an increase in protein synthesis, muscle mass formation, and therefore both types of exercise training (Moderate-intensity continuous [MICT] + resistance training [RT]) are usually referred to in the literature as combined exercise or concurrent exercise (MICT+RT) (8). Among the main effects or benefits of exercise training in CS individuals, particularly in terms of reducing anxiety, depressive symptoms, fatigue, quality of life, lymphedema, and physical function (4). It has also been reported that there is only “moderate” evidence on the effects of exercise in CS at the level of bone health,

and sleep, but worryingly, there is insufficient evidence in favor of physical exercise at the level of vascular function, falls, cognitive function, and pain, among other health parameters (sexual function, nausea, peripheral neuropathies). The potential results of the project will ultimately translate into greater technical, scientific and management knowledge to be able to analyze the increase in the offer of physical exercise programs or workshops for CS persons in Chile. The latter should translate into an improvement not only in the physical condition and health of CS people, but also in a lower risk of relapsing into cancer, mental illnesses (depression) and, of course, a reduction in mortality. From here, high-intensity interval training, a particular exercise modality of brief intense exercise intervals have been poorly studied in breast CS (9). Similarly, RT using lower exercise intensities (i.e., one repetition maximum test [1RM] load of $\leq 60\%$ of 1 RM) have been also little tested for cardio-vascular (i.e., PWV, FMD, and cIMT) and metabolic health in breast CS women. Preliminary evidence show that concurrent exercise training decrease blood pressure, and that HIIT also decrease arterial stiffness in adult women. Sawyer et al. reported that 8-weeks of HIIT was superior to MICT for increasing FMD in HIIT vs MICT ($\Delta +8.9$ vs. 5.1%) (10). Deisenroth et al. (11) showed that 12-week of HIIT (four sets [4 min] intervals at 80-90% HR_{max} with resting periods of 60-70% HR_{max} cycling) reduced minimally PWV ($-0.1\text{ m}\cdot\text{s}^{-1}$) in hypertensive older adults (11). One-year of HIIT (60 s interval, 60 s of resting at 90% of the reserve oxygen consumption) decreased both systolic [SBP] ($\Delta -6.5$)/diastolic [DBP] blood pressure ($\Delta -4.2\text{ mmHg}$), and decreased cIMT_{av} ($\Delta -0.95\text{ mm}$) (12).

Thus, concurrent training of both HIIT plus RT in lower 1RM intensities could promote potential benefits for both cardiovascular health and metabolic and physical condition parameters of breast CS women, however, there is scarcity of studies about this

exercise modalities in patients who are CS and that have been exposure to higher and lower chemotherapy doses (13-15).

RESEARCH PROBLEM: Despite the “solid” evidence in favor of the effects of exercise training in breast CS to improve variables such as anxiety, depressive symptoms, fatigue, quality of life, lymphedema and physical function, however, unfortunately, the effects of exercise training on cardio-vascular and metabolic variables, there is still unknown the effects of concurrent exercise training including HIIT plus RT in lower 1RM doses in CS women at level of their cardio-vascular and metabolic health.

This is due to the fact that year after year there is an increase in the number of early diagnoses, as well as an increase in the number of CS with a successful completion of their breast cancer treatment (Radiotherapy, Chemotherapy, Hormonal Therapy), which also leads as an effect to an inherent increase in the number of CS persons, requiring the insertion of this population back into active life. Another effect of the scientific rationale lies in the scarce offer of physical activity and/or exercise training programs for this population of women between 40 and 70 years of age, which would be significantly overcome with the application of the present intervention project that would report cardiovascular, metabolic, physical condition, quality of life and eating patterns variables. **OBJECTIVES; GENERAL:** To determine the effects of traditional therapy added to physical exercise on cardio-vascular, metabolic and physical fitness in female breast cancer survivors who received lower (≤ 7 sessions) and higher (≥ 8 sessions) of chemotherapy.

This study will follow the CONSORT guidelines for randomised trials, will be developed in accordance with the Declaration of Helsinki (2013), and has been approved by the BIOETICAL COMMITTEE OF UNIVERSIDAD ANDRES BELLO (Approval 005/2024 of April 12th). **Design:** An experimental clinical randomized study. **Methods:**

Adult women breast cancer survivors who have undergone all the stages related to breast cancer treatment (chemotherapy, radiotherapy, hormone therapy). The study will be carried out in the facilities of the Exercise Physiology Laboratory of the Exercise and Rehabilitation Sciences Institute of the Universidad Andrés Bello, Concepción city, from different community cancer survivors' social groups of the Concepcion, Chile will be invited to participate of this study. The groups will be randomly allocated to an experimental group of high chemotherapy exposure (EG-HCHT, n=15) or to an experimental group of low chemotherapy exposure (EG-LCHT, n=15), that will adhere to 6-weeks of an exercise training program of concurrent training of HIIT plus RT three weekly.

Inclusion criteria: a) breast cancer diagnosed, b) with or without chemotherapy treatment, c) normal weight body mass index [BMI] 18.6 to 24.9 or overweight/obesity condition by BMI 25.0 to 39.9 kg/m², d) age 30 to 75 years, e) with or without other associated co-morbidities (diagnosed of elevated fasting glucose, prediabetes or diabetes, hypertension or prehypertension, or metabolic syndrome, fatty liver or hypercholesterolemia or screened by our research team), f) with or without hormonal therapy, and g) with or without other pharmacotherapy for specific muscle-groups such as morphine patches, morphine droplets or other pharmacological therapy for SOS pain treatment. **Exclusion criteria:** a) history of abnormal ECG, or diagnosis of other cardiovascular condition/history other than hypertension, vasculopathy, b) history of uncontrolled stage 3 of hypertension or hypertensive crisis, c) diabetes complications such as varicose ulcers, nephropathies, d) skeletal muscle abnormalities (e.g., knee, or hip arthrosis, muscle pain), e) using weight loss treatment/pharmacotherapy or being active in exercise training programs (or within the past three months), and f) use other pharmacotherapy that can influence body weight loss, g) respiratory disease type (chronic

obstructive disease), h) kidney disease, i) pregnancy, and j) smoking behaviour or dependence on other substances.

REFERENCES

1. MINSAL. Tabla de resumen de mortalidad por causa, según sexo y región 2023 [Available from: <https://informesdeis.minsal.cl/SASVisualAnalytics/>].
2. WHO. WHO Guidelines on Physical Activity and Sedentary Behaviour. Geneva; 2021.

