
16. Cohen J. *Statistical Power Analysis for the Behavioral Sciences*. 2013.

STATISTICAL ANALYSIS PLAN (SAP): Data will be presented as the mean \pm standard deviation (SD). Normality and homoscedasticity assumptions will be tested by using Shapiro-Wilk tests and homoscedasticity by the Levene test. For those outcomes with normal distribution, paired *t*-test was applied to test differences, while to those with no normal distribution, unpaired *t*-test was applied. Cohen's *d* effect size (<0.2 = negligible, $0.2-0.49$ = small, $0.5-0.79$ = moderate, ≥ 0.8 = large) for interactions that showed statistically significant (16). Each delta (Δ), pre-post changes, of main and secondary outcomes will be calculated in all groups. To test the associations among main vascular outcomes (PWV, FMD, cIMT_{av}, cIMT_{max}) with anthropometric, body composition, metabolic, cardio-vascular outcomes, and physical fitness outcomes, simple linear regression (to parametric) with R² prediction percentage, or the *Rho* Spearman nonparametric correlation (r_s =) will be applied. Statistical analyses will be developed using Prism 8.0 software (Graph Pad, San Diego, CA, United States), and the SPSSTM software 29 version for Windows (IBM SPSS Inc., Chicago, IL, USA). The alpha level will be fixed at ($P \leq 0.05$) for all statistical significance.

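### Time since the end of treatment is neither limited nor used in the analysis, so it could confound the comparison of higher- and lower-chemotherapy groups

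*Combined protocol and SAP*

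**What the plan says.** **Population.** The Methods describe "Adult women breast cancer survivors who have undergone all the stages related to breast cancer treatment (chemotherapy, radiotherapy, hormone therapy"). Treatment has to be over, but nothing says how long ago. The inclusion criteria add "b) with or without chemotherapy treatment" and "f) with or without hormonal therapy", neither with a time condition. The only look-back given in months is in exclusion criterion e, "using weight loss treatment/pharmacotherapy or being active in exercise training programs (or within the past three months"), and it does not concern cancer treatment.

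**Groups.** The general objective refers to "female breast cancer survivors who received lower (≤ 7 sessions) and higher (≥ 8 sessions) of chemotherapy". The Methods say women are "randomly allocated to an experimental group of high chemotherapy exposure (EG-HCHT, n=15) or to an experimental group of low chemotherapy exposure (EG-LCHT, n=15"), and both groups follow the same programme: "that will adhere to 6-weeks of an exercise training program of concurrent training of HIIT plus RT three weekly". There is no non-exercise group.

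**Analysis.** The SAP states that "Each delta (Δ), pre-post changes, of main and secondary outcomes will be calculated in all groups". It names paired and unpaired t-tests, chosen by normality, and simple regression or Spearman correlation for associations between outcomes. It names no covariate, stratification factor or matching variable, and time since treatment does not appear in it.

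**The concern.** Since every woman trains, the only between-group question this design can address is whether the response differs between survivors with more and with fewer past sessions. Session count is a fact of each woman's history. The word randomly in the Methods cannot make it assignable, and so cannot balance anything that travels with it. Time since treatment is one such variable. As written, a woman a few weeks past treatment and a woman many years past it are both eligible and are classified by session count alone.

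Suppose time since treatment is related to the six-week change, and the groups differ in it. A difference in recency would then appear as a difference in response by chemotherapy exposure. Nothing in the plan would reveal this, because it does not commit to recording or reporting the variable.

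**Working it through.** **1. What can be reproduced.** The documents give 15 women per group without power, effect size, SD or dropout, so there is no calculation to reproduce, and no figure in the plan is called wrong here.

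**2. Inputs.**
- From the documents: n = 15 per group; alpha 0.05.
- Assumed: two-sided test, since the SAP does not state sidedness; a gap *g* between the group means of (log) time since treatment, in within-group SDs, of 0.5 to 1; a within-group correlation *r* of that time with the change score of 0.1, 0.3 or 0.5; no true exposure effect. The documents give no data on *g* or *r*.

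**3. Spurious difference.** With the change score scaled to within-group SD 1, the false shift between groups is *g* × *r*. The unadjusted two-group t-test has 15 + 15 − 2 = 28 degrees of freedom, and its noncentrality is *g* × *r* × √(15/2) = *g* × *r* × 2.739. The noncentral t distribution gives the rejection rates below.

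| g (SD) | r | Shift g × r (SD) | Noncentrality | Unadjusted rejection rate |
|---|---|---|---|---|
| 0.5 | 0.1 | 0.05 | 0.137 | 5.2% |
| 1.0 | 0.1 | 0.10 | 0.274 | 5.8% |
| 0.5 | 0.3 | 0.15 | 0.411 | 6.8% |
| 0.5 | 0.5 | 0.25 | 0.685 | 10.1% |
| 1.0 | 0.3 | 0.30 | 0.822 | 12.5% |
| 1.0 | 0.5 | 0.50 | 1.369 | 26.2% |

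A simulation of 20,000 trials per cell agrees for the last four rows: 6.8%, 10.2%, 12.3% and 26.8%.

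**4. With time as a covariate.** In the same simulated trials, a linear model with group and time rejects in 4.8% to 5.0%. This return to the nominal level is by construction, since the fitted model is the one that generated the data. It shows what adjustment can do when the form is right, not that it will be right here.

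**5. Price of adjustment.** With equal groups, a gap of *g* within-group SDs inflates the variance of the adjusted group effect by 1 + *g*²/4. At *g* = 1 this is 1.25, so the standard error rises by √1.25 − 1 = 12%. At *g* = 2 it is 2.0, so the standard error rises by √2 − 1 = 41%. Both are before any gain from variance that time explains.

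**6. Within-group tests.** Drift unrelated to training goes straight into a pre-post test. For a paired t-test with n = 15 (14 degrees of freedom, noncentrality *d* × √15), an assumed drift of 0.2, 0.5 or 0.8 SD of the change score gives significance in 11%, 44% or 82% of trials with no training effect. The between-group covariate does not address this.

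**The case against.** The strongest reply is that every quantity behind the size is assumed. There are no time-since-treatment data, no correlation with change, and no evidence of imbalance or of its direction. If most recruits are years past treatment, which recruitment from community survivors' groups leaves quite possible, drift over six weeks may be small, and at *r* = 0.1 the inflation nearly vanishes. All of this stands, and it limits the point to a possible bias of unknown size.

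Three stronger readings are tempting and are not supported.
- A reader might infer that recently treated women will recover over six weeks without training, and that references 13-15 show this. Only their titles are visible. The Background cites them for higher and lower chemotherapy doses; two titles name long-term effects and the third concerns preventing cardiac damage. Lasting effects do not imply spontaneous recovery within six weeks.
- A reader might infer that the SAP tests raw changes between groups. It says that they will be calculated. The choice between paired and unpaired tests rests on normality, and interactions are mentioned without a model, so no between-group test is clearly specified. That comparison has to be defined before a covariate can enter it.
- A reader might take time since the last chemotherapy session as the obvious covariate. Women without chemotherapy are eligible and presumably fall in the group with 7 or fewer sessions. They have no such date, and a complete-case model would drop women from that group alone.

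It is also fair to say that age (30 to 75), hormonal therapy and comorbidity are equally unbalanced, and that this point follows from the larger fact that exposure is not assignable. That does not remove it. Describing the study as a comparison of two existing cohorts would make recording confounders more necessary.

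**Conclusion.** The point holds in a limited form. It is established from the text that eligibility sets no window since the end of treatment, that the SAP names no covariate, and that grouping by past session count leaves time since treatment unbalanced by design. It follows that recency could confound the exposure contrast. It does not follow that it will, or which group would be favoured.

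The rates of about 7% to 26%, against a nominal 5%, rest wholly on the assumed gap of 0.5 to 1 SD and correlation of 0.3 to 0.5. A correlation near 0.1 brings them to 5% to 6%. The change is worth making because it is cheap and protects the only between-group contrast available. It does not rescue the within-group results: without a non-exercise group, natural recovery and training effect cannot be told apart.

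**What to change.** 1. Record for every woman the date primary treatment ended: the last chemotherapy or radiotherapy session, or the end of the last completed primary treatment if she had neither. This is defined for women without chemotherapy. The documents do not name the source of session counts, so the sponsor should state where both items come from.
2. Tabulate time since that date by group.
3. In the SAP, specify the between-group comparison as a linear model of the pre-post change on exposure group plus log months since the end of primary treatment, with the unadjusted contrast as secondary.
4. State in advance that if the groups barely overlap in time, the exposure contrast will be reported as not interpretable.
5. State in the report that the adjustment does not separate natural recovery from training effect within a group.

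**Cost.** One date per woman, one table row and one degree of freedom (28 becomes 27). The standard error widens if time is tied to group, by about 12% at a 1 SD gap and 41% at 2 SD, before any gain from explained variance. Recruitment, programme and sample size are unchanged.

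### Past chemotherapy exposure cannot be randomly allocated, and with both groups exercising the study cannot isolate a causal effect of exercise

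*Combined protocol and SAP*

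**What the plan says.** The Design statement calls the study "An experimental clinical randomized study", and the sentence before it says "This study will follow the CONSORT guidelines for randomised trials". The Methods describe the allocation as follows: "The groups will be randomly allocated to an experimental group of high chemotherapy exposure (EG-HCHT, n=15") or to a low-exposure group, also of 15.

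The general objective defines the two exposure levels by treatment history, as women "who received lower (≤ 7 sessions) and higher (≥ 8 sessions) of chemotherapy". The Methods describe the population as survivors "who have undergone all the stages related to breast cancer treatment", and list chemotherapy among those stages. Inclusion criterion b nevertheless admits women "with or without chemotherapy treatment".

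Both groups carry the label experimental group. One intervention is described, for groups "that will adhere to 6-weeks of an exercise training program of concurrent training of HIIT plus RT three weekly". No usual-care, delayed-start or alternative-exercise arm appears anywhere. The objective reads: "To determine the effects of traditional therapy added to physical exercise on cardio-vascular, metabolic and physical fitness in female breast cancer survivors". The SAP plans pre-post deltas in all groups, paired or unpaired t-tests, and simple regressions or correlations. It states no adjustment for differences between the exposure groups.

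**The concern.** Random allocation means that chance decides which condition a woman receives after she enters the study. Here the condition named in the allocation sentence is something that happened to her earlier, so there is nothing left to assign. The randomised design label and the randomised-trial reporting standard both rest on that sentence.

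Two kinds of claim are at stake. First, a randomised label invites readers to treat a difference between the high- and low-exposure groups as unconfounded. It may instead reflect whatever determined the number of sessions, for example disease extent, age, hormone therapy or comorbidity. Second, the title and objective speak of effects of exercise, but every woman exercises. Change within a cohort mixes exercise with the passage of time, familiarity with the fitness tests and concurrent treatment.

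**Working it through.** **What the text allows**

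| Element | Where | What it fixes |
|---|---|---|
| Groups defined by sessions received, ≤ 7 v ≥ 8 | Objectives; General | Exposure lies in the past |
| Women have completed treatment | Methods, population | Exposure is settled before enrolment |
| Random allocation to high or low exposure | Methods, allocation | Contradicts the two rows above |
| One HIIT plus RT programme, both groups experimental | Methods, intervention | No contrast in exercise |
| Deltas in all groups | SAP | Within-cohort change is estimable |

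Three charitable readings were tried.

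- Randomisation within exposure strata, to exercise or control, would be valid. No such arms or strata are described.
- If the exercise clause applied only to the low-exposure group, exercise would be completely confounded with exposure.
- Random might mean random sampling. But the text says allocated, and women are invited through community groups.

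None rescues the label.

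**Possible size of the bias**

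The plan offers no target effect, SD or sample-size derivation, so it has no figure to reproduce. Only n = 15 per group comes from the documents. The alpha of 0.05 is also stated, but its sidedness is not, and two-sided is assumed. Imbalance, correlation and drift below are assumptions. All effects are in units of the SD of change.

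*Between cohorts (unpaired t-test on change scores).* Bias = covariate imbalance (SD) × correlation of the covariate with change. Noncentrality = bias × √(15/2), with 28 degrees of freedom and no true exposure effect.

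| Imbalance × correlation | Bias | Noncentrality | Rejection rate |
|---|---|---|---|
| 0.5 × 0.2 | 0.10 | 0.274 | 5.8% |
| 0.75 × 0.2 | 0.15 | 0.411 | 6.8% |
| 0.5 × 0.5 | 0.25 | 0.685 | 10.1% |
| 0.75 × 0.5 | 0.375 | 1.027 | 16.8% |

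A stable confounder unrelated to change adds no bias to this comparison.

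*Within one cohort (paired t-test, n = 15).* Noncentrality = drift × √15, with 14 degrees of freedom and no exercise effect.

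| Non-exercise drift | Noncentrality | Rejection rate |
|---|---|---|
| 0.1 | 0.387 | 6.5% |
| 0.2 | 0.775 | 11.2% |
| 0.3 | 1.162 | 19.2% |

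*Precision (95% CI half-width).*

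- Between cohorts: 2.048 × √(2/15) = 0.748 SD.
- Within one cohort: 2.145 / √15 = 0.554 SD.

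A larger sample would narrow these intervals. It would not turn a contrast in chemotherapy history into an exercise effect.

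**The case against.** No reading was found that makes the allocation sentence correct, and the sentence is complete, so this is neither a redaction nor an extraction fault. The strongest counter-arguments concern scope and weight.

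- **The missing control is partly a design choice.** The documents never promise a non-exercise arm, and two exercised cohorts can describe response by chemotherapy history. This stands. The missing arm is a limit on what may be claimed. The error is the randomised label, together with an objective that outruns the design.
- **The causal objective is partly inferred.** The phrase about traditional therapy added to exercise is unclear. It is read here, with the study title, as the effect of exercise. That is reasonable because both use the word effects, but it is an interpretation.
- **Zero sessions already satisfies ≤ 7.** Arithmetically it does. But the objective speaks of chemotherapy received and the population sentence lists it among the stages undergone, so criterion b conflicts with both and a stated rule is still needed.
- **The rejection rates rest on assumptions.** They do, and the low ends are close to nominal. The SAP also assigns the unpaired test only to non-normal outcomes and never clearly says that deltas are compared between groups. Test learning bears mainly on effort-based measures rather than on the vascular outcomes. The figures show what could happen, not what will.
- **The exclusions help.** Barring recent exercise training, weight-loss treatment, smoking and several diseases narrows some routes of bias. Criterion e still admits many comorbidities, so confounding remains.

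**Conclusion.** The concern holds, and correction is essential. The randomised design label, the random-allocation sentence and the randomised-trial reporting claim are wrong as written, because exposure is fixed before enrolment. This conclusion follows from the text and does not depend on any calculation.

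The study can support an estimate of six-week change in each cohort and an observational difference in change between cohorts. It cannot isolate a causal effect of exercise, or an unconfounded effect of chemotherapy exposure. The illustrative false-positive rates, up to 16.8% between cohorts and 19.2% within one against a nominal 5%, depend wholly on the assumed imbalance, correlation and drift.

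**What to change.** 1. Replace random allocation with classification by documented number of chemotherapy sessions. State whether women with no chemotherapy count as low exposure, and reconcile criterion b with the population sentence.
2. Describe the design as a non-randomised two-cohort pre-post study, and name a reporting standard for non-randomised studies in place of the randomised-trial one.
3. Restate the objective as six-week change during exercise and its difference between exposure cohorts, with no causal claim against traditional therapy alone.
4. Specify in the SAP that the between-cohort difference in change is reported with its 95% CI as observational. Any covariate adjustment, for example for age, is a sensitivity analysis that does not remove confounding.

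The cost is protocol wording, one classification rule, a small SAP amendment and an optional sensitivity model. No extra women or visits are needed. Because the stated design and objective of an ethics-approved study change, the investigators should check whether the committee must be told. The price is a weaker claim, but a correct one.

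Keeping the randomised label and a causal objective would require randomising something assignable, such as immediate against delayed start, stratified by exposure. That is a redesign, with extra assessments and its own sample-size justification. At 15 v 15, a two-sample t-test has 26% power at d = 0.5 and 56% at d = 0.8, and reaches 80% only at d of about 1.06. For 80% power, d = 0.8 needs 26 per arm and d = 0.5 needs 64. Thirty women over four start-by-exposure cells gives 30/4 = 7.5, so 7 or 8 per cell.

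### The Research Problem and inclusion criterion d) give different age ranges, and the SAP has no means of separating age from the chemotherapy-group comparison or the vascular associations

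*Combined protocol and SAP*

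**What the plan says.** The Research Problem describes a scarce offer of "exercise training programs for this population of women between 40 and 70 years of age", a gap "which would be significantly overcome with the application of the present intervention project". In Methods, inclusion criterion d) reads "age 30 to 75 years". No other age limit appears, and no text links or explains the two ranges. The general objective speaks of "female breast cancer survivors who received lower" or higher numbers of chemotherapy sessions, and Methods opens with "Adult women breast cancer survivors who have undergone all the stages related to breast cancer treatment". Neither gives an age band.

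The two groups of 15 are named by high and low chemotherapy exposure. The general objective puts the cut at 7 or fewer versus 8 or more sessions. Methods calls the allocation random.

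The SAP names paired and unpaired t-tests for differences and calculates pre-post changes for each outcome. It relates PWV, FMD and cIMT to anthropometric, body composition, metabolic, cardiovascular and fitness outcomes by simple linear regression or Spearman correlation. It mentions no covariate, stratification or matching, and age is not used in any analysis.

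**The concern.** Two current statements about whom the project concerns do not agree, so a reader cannot tell whether the results are meant for women aged 40 to 70 or 30 to 75.

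The larger question is what the plan does with age once a wide range is admitted. The number of chemotherapy sessions a woman has already received is part of her history. Calling the allocation random does not change that, so randomisation cannot be relied on to balance age between the groups. If treatment history and age are related among the women enrolled, a difference between the groups could partly be a difference in age. In the association analyses, a vascular measurement and a fitness measurement that both vary with age will be correlated even if neither affects the other. One-predictor methods cannot tell these explanations apart.

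**Working it through.** **1. The two ranges.** Inputs: 30 and 75 (inclusion criterion d), 40 and 70 (Research Problem).
- Years below 40: (40 − 30)/(75 − 30) = 10/45 = 22.2%.
- Years above 70: (75 − 70)/45 = 5/45 = 11.1%.
- Total outside: 15/45 = 33.3% of the span. Counted as whole-year ages, it is 15/46 = 32.6%.

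The documents give no figure of their own to reproduce and no age distribution. The share of the 30 women who fall outside 40 to 70 could be anything from 0 to 100%.

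**2. The between-group comparison of changes.** Let D be the difference in mean age between the groups and g the change in an outcome's pre-post delta per year of age. An unadjusted comparison of deltas is then off by g × D. If g = 0, meaning that age affects only the level of the outcome, there is no bias, because age is effectively constant over the 6 weeks. If g is not zero, the bias grows with D. The documents give neither quantity. As a yardstick, the SAP counts d below 0.2 as negligible. To produce a shift of 0.2 SD:
- with D = 5 years (assumed), g must be 0.2/5 = 0.04 SD per year;
- with D = 10 years (assumed), g must be 0.2/10 = 0.02 SD per year.

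A t-test has no term for g, so it can neither detect nor remove this.

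**3. The association analyses.** Suppose a vascular measurement and a predictor are related only through age, each correlating r with age. Their correlation is then r × r. The values of r are assumptions, because the documents give none. With n = 30 and two-sided alpha 0.05 (the SAP does not state sidedness), significance needs |r| above 2.048/√(2.048² + 28) = 0.361. The chance of exceeding it follows from the Fisher z approximation, with standard error 1/√27 = 0.192 and atanh(0.361) = 0.378:

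| Correlation of each with age (assumed) | Induced correlation | Chance that a nominal 5% test rejects |
|---|---|---|
| 0.3 | 0.09 | 7% |
| 0.4 | 0.16 | 13% |
| 0.5 | 0.25 | 26% |

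For r = 0.5, for example: (0.378 − 0.255)/0.192 = 0.64, and the upper tail beyond 0.64 is 0.26. Simple regression has one predictor and Spearman correlation has none to adjust for, so as planned the induced part stays in the estimate.

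**4. What adjustment costs.** With 30 women, an unadjusted comparison of deltas has 30 − 2 = 28 degrees of freedom. ANCOVA with group, baseline value and age has 30 − 4 = 26. The two-sided critical value moves from 2.048 to 2.056. Adding age to a one-predictor regression takes 28 to 27, and the critical value becomes 2.052.

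**The case against.** The strongest reply is that the mismatch is one of wording. The 40 to 70 band occurs once, in a rationale sentence. The objective, title and opening of Methods set no such band, and criterion d) is the only operating rule, so nobody recruiting would be in doubt. The wider range also contains the narrower one. All of this stands, and it is why the mismatch needs no more than reconciling.

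The reply continues that the main analyses are pre-post. A stable effect of age on the level of an outcome cancels within each woman, so paired tests and deltas are not distorted by it. This also stands. Age matters for the comparison of deltas only if it alters the response to training. It matters for the associations mainly if levels rather than deltas are related, and the SAP does not say which will be used. Nor do the documents state that the vascular outcomes depend on age. Age is therefore a plausible confounder here, not a demonstrated one.

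Finally, groups formed by past chemotherapy are open to confounding at any age range. That is true. It is a reason to adjust for age whichever range is kept, and a reason not to expect narrower eligibility to solve the problem.

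**Conclusion.** The point holds as a modest one with an inexpensive remedy. The two age ranges conflict and must be reconciled. The SAP also lacks any method that could separate age from the group comparison or the vascular associations, although the groups are not formed by anything that could be randomised. The size of any bias cannot be computed from the documents. The 7% to 26% rejection rates rest on assumed correlations of 0.3 to 0.5 with age, 30 complete women and a two-sided 5% test. No stated sample size or alpha is affected.

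Four stronger readings are not supported:
- A reader might infer that a third of participants will lie outside the intended population. The third is a share of calendar years, and no age distribution is given.
- A reader might compare the age variance of the two ranges and take the ratio as the size of the harm. That ratio depends wholly on assuming that ages are evenly spread.
- A reader might conclude that eligibility should be narrowed to 40 to 70, or the main comparisons repeated in that subset. The documents do not show which range is intended, and a subset of groups of 15 would add underpowered tests.
- A reader might argue that younger women bring menstrual-cycle effects into FMD. No assessment dates are given, a cycle length would have to be assumed, and women over 40 may also menstruate.

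**What to change.** 1. State one age range in both the Research Problem and inclusion criterion d), or explain why they differ. The choice is the sponsor's.
2. In the SAP, compare changes between the chemotherapy groups with age as a covariate, for example by ANCOVA with group, baseline value and age.
3. In the analyses of PWV, FMD and cIMT, replace simple regression with multiple regression including age, and Spearman correlation with partial Spearman correlation given age. Say whether levels or deltas are being related.
4. Report age by group, so that readers can see how far it differs.

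The cost is a text edit and one or two degrees of freedom with about 30 women. Age must already be recorded to apply criterion d), so no new data are needed. Adjustment deals with age only. Other differences linked to treatment history would remain, and the results should be worded accordingly.
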